### 5.3 Randomization and Blinding

This is a randomized, double-blind, placebo-controlled study. For the Double-Blind Treatment Period, subjects who meet the inclusion criteria and exclusion criteria will be randomized to receive either avatrombopag 60 mg or placebo in a 2:1 ratio at the Baseline Visit. Randomization will be stratified by the number of chemotherapy agents the subject is receiving (1, ≥2 permissible chemotherapy agents [nucleoside analog, including gemcitabine and fluorouracil; carboplatin or cisplatin; anthracycline; or alkylating agent]). Randomization assignment will be performed using interactive response technology (IRT). Following randomization, IP will be dispensed in a double-blind manner. The Sponsor and designated clinical site personnel (Investigator and study coordinator) will be blinded to the treatment group for each subject. Subjects will also be blinded to the treatment they receive.

## **5.4 Breaking the Blind**

At the initiation of the study, the Investigator will be instructed on the method for breaking the blind. The blind is not to be broken during the study unless considered necessary by the Investigator for emergency situations for reasons of subject safety. Unblinding at the clinical site for any other reasons will be considered a protocol deviation. The Investigator should contact the Medical Monitor before breaking the blind, if time permits. When the blind is broken, the reason must be fully documented.

## **5.5 Drug Supplies**

### **5.5.1 Formulation and Packaging**

Avatrombopag will be provided as film-coated tablets, with each tablet containing avatrombopag maleate (equivalent to 20 mg of avatrombopag) and the following excipients: lactose monohydrate, colloidal silicon dioxide, crospovidone, magnesium stearate, microcrystalline cellulose, and Opadry II 85F42244.

Matching placebo tablets, containing lactose monohydrate (23.6 mg), will be provided.

Investigational product will be packaged in blinded blister packages, each containing 15 tablets.

For the optional OLE Period, avatrombopag will be packaged in open-label blister packages, each containing 15 tablets of avatrombopag.

### **5.5.2 Investigational Product Dispensing**

The Investigator or designee will provide subjects with sufficient IP to complete each 5-day course of study drug during the Double-Blind Treatment Period (each 5-day course to be dispensed on separate occasions as appropriate). If subjects continue into the optional OLE Period, the Investigator or designee will provide subjects with additional IP to complete the optional OLE Period.

### **5.5.3 Investigational Product Administration**

Subjects randomized to the investigational arm will receive 60 mg avatrombopag (3 × 20 mg tablets) for oral administration once daily for 5 days prior to Chemotherapy Day and for 5 days immediately following Chemotherapy Day during the Double-Blind Treatment Period. Subjects randomized to the control arm will receive matching placebo tablets.

Subjects in the optional OLE Period will receive 60 mg avatrombopag (3 × 20 mg tablets) for oral administration once daily for 5 days prior to Chemotherapy Day and for 5 days after Chemotherapy Day.

At scheduled study visits, IP may be administered at the site or the subject may self-dose except for Visits 3 and 5 when subjects will be dosed at the site and serial PK samples will be collected pre- and post-dose of IP. Subjects will self-dose at all other times. Subjects will be instructed to take IP with food.

During the study, if the subject has a platelet count  $>400 \times 10^9/L$ , IP dosing will be stopped temporarily. Dosing may be restarted following discussion with the Medical Monitor.

The number of tablets to be taken will be three 20 mg avatrombopag tablets or 3 matching placebo tablets once daily.

Actual date and time of chemotherapy doses will also be captured.

#### **5.5.4 Treatment Compliance**

At scheduled study visits, IP may be administered at the site or the subject may self-dose except for Visits 3 and 5 when subjects will be dosed at the site and serial PK samples will be collected pre- and post-dose of IP. Subjects will self-dose at all other times. When taking IP at home for the double-blind phase of the study, subjects will be asked to record the date and time of each IP dose in the dosing diary.

Compliance with IP administration will be assessed by counting returned IP packages and any unused IP in addition to reviewing the dosing diary entries of IP intake. Any discrepancies between returned IP number and dosing in the dosing diary will be discussed with the subject for whom a discrepancy was seen and recorded in the source documents. Number of tablets dispensed and number of tablets returned will be recorded on the appropriate drug accountability eCRF.

#### **5.5.5 Storage and Accountability**

Investigational product should be stored at controlled room temperature (20°C to 25°C/68°F to 77°F) with excursions permitted to 15°C to 30°C (59°F to 86°F) in a secure location and in the containers provided.

Records will be maintained indicating the receipt and dispensation of all IP supplies. At the conclusion of the study, any unused IP will be returned to the Sponsor or the Sponsor's designee or may be destroyed at the site if appropriate procedures are in place. If no supply remains, this will be indicated in the Drug Accountability Log.

### **5.6 Prior and Concomitant Medications and/or Procedures**

#### **5.6.1 Excluded Medications and/or Procedures**

The following medications and/or procedures are excluded:

- Use of vitamin K antagonists;
- Use of thrombopoietin receptor agonists or recombinant human thrombopoietin;
- Use of moderate or strong inducers of CYP2C or CYP3A4/5 (see [Appendix C](#)); and
- Currently enrolled in another clinical study with any investigational drug or device within 30 days of Screening; however, participation in observational studies is permitted.

#### **5.6.2 Allowed Medications and/or Procedures**

- Use of packed red blood cell transfusions, erythropoietin, or granulocyte-colony stimulating factor, as ordered by the managing oncology service, is acceptable and does not preclude participation; and
- Use of low molecular weight heparin, Xa inhibitors, or thrombin inhibitors is allowed.

### **5.6.3 Documentation of Prior and Concomitant Medication Use**

All concomitant medications (including concurrent therapies and concurrent procedures) will be documented from the time of informed consent to the Follow-Up Visit. Dose, indication for administration, and dates of medication administration will also be captured in source documents and on the appropriate eCRF.

## 6 STUDY PROCEDURES

A schedule of procedures in tabular format is provided in [Table 1](#), [Table 2](#), and [Table 3](#) in [Appendix A](#).

Local laboratories may be used to determine study eligibility; however, for study analysis and reporting purposes, only values determined at a central laboratory will be used with the exception of platelet count. Platelet count analyses will be performed using local laboratory results. Local laboratories may be used if immediate results are clinically needed (eg, Baseline Visit).

### 6.1 Informed Consent

Prior to conducting any study-related activities, written informed consent must be signed and dated by the subject. See [Section 12.4](#) for additional information on informed consent.

### 6.2 Cycle X (Qualifying Chemotherapy Cycle)

#### 6.2.1 Screening (Visit 1, Day -28 to Day -1)

The Screening Visit may be combined with the Baseline Visit on the day prior to IP treatment (Day -1).

The following procedures will be performed at the Screening Visit:

- Obtain informed consent prior to screening procedures;
- Contact IRT to register the subject in the study
- Conduct eligibility assessment based on inclusion/exclusion criteria;
- Obtain demographics (including race), and medical history (to include chemotherapy and cancer history);
- Assess functional status using the ECOG Performance Status Scale;
- Record concomitant medications;
- Assess adverse events;
- Perform full physical examination;
- Record vital signs (includes height, weight, body temperature, blood pressure, and pulse rate); and
- Perform pregnancy test (serum or urine) for female subjects of childbearing potential only;
- Collect blood samples for the following assessments (if Screening Visit occurs on the same day as the Baseline Visit, only the Baseline laboratory assessments should be performed):
  - Hematology (including platelet counts). Local platelet counts may be repeated as needed; and
  - Serum chemistry

### **6.2.2 Baseline Visit (Visit 2, First Day [or -1 Day] of the 5-day Investigational Product Treatment)**

The Baseline Visit may occur one day prior to IP treatment, and may be combined with the Screening Visit.

Eligible subjects will receive either avatrombopag or placebo once daily for 5 days prior to Chemotherapy Day in Cycle X + 1. The following procedures will be performed at the Baseline Visit prior to IP dosing:

- Conduct eligibility assessment based on inclusion/exclusion criteria;
- Contact IRT to randomize the subject;
- Perform International Society on Thrombosis and Haemostasis (ISTH) bleeding assessment (see [Appendix D](#));
- Record concomitant medications;
- Assess adverse events;
- Perform symptom-directed physical examination (if not previously performed within 1 week of Baseline Visit);
- Record vital signs (includes weight, body temperature, blood pressure, and pulse rate). Only Screening vital signs will be recorded if combined with the Screening Visit;
- Collect blood samples for the following assessments:
  - Hematology (including platelet counts);
  - Coagulation; and
  - Serum chemistry;
- Perform pregnancy test (serum or urine) for female subjects of childbearing potential only;
- Assess chemotherapy dose modifications/schedule;
- Dispense IP;
- Dispense dosing diary; and
- Administer or self-dose IP with food, if the Baseline Visit occurs on the first day of the 5-day IP treatment.

### **6.2.3 Pre-Chemotherapy Investigational Product Treatment (Visit 3, Last Day of the 5-day Investigational Product Treatment)**

The following procedures will be performed on the last day of the 5-day pre-chemotherapy IP treatment at Visit 3:

- Contact IRT;
- Perform ISTH bleeding assessment (see [Appendix D](#));
- Record concomitant medications;
- Assess adverse events;

- Collect blood samples for the following assessments:
  - Hematology (including platelet counts); and
  - PK sampling at pre-dose (within 30 minutes of IP dosing) and 0.5 to 2, 2 to 4, and 4 to 6 hours post-dose. Each sample must be collected at least one hour apart from adjacent samples.
- Assess chemotherapy dose modifications/schedule;
- Assess whether subject required platelet transfusion;
- Administer IP in the clinic with food after the first PK sampling;
- Review dosing diary; and
- Collect unused IP, if applicable.

### **6.3 Double-Blind Treatment Period (Cycle X + 1)**

#### **6.3.1 Chemotherapy Day (Visit 4, Cycle X + 1 Day 1 to 3)**

The following procedures will be performed on Cycle X + 1, Day 1 at Visit 4 prior to chemotherapy dosing:

- Perform ISTH bleeding assessment (see [Appendix D](#));
- Record concomitant medications;
- Assess adverse events;
- Perform symptom-directed physical examination;
- Record vital signs (includes blood pressure and pulse rate);
- Collect blood samples for the following assessments:
  - Hematology (including platelet counts); and
  - Serum chemistry;
- Assess chemotherapy dose modifications/schedule; and
- Assess whether subject required platelet transfusion.

The following procedures will be performed post-chemotherapy dosing (these procedures will be performed on the last Chemotherapy Day of the cycle):

- Dispense IP; and
- Dispense dosing diary.

#### **6.3.2 Post-Chemotherapy Investigational Product Treatment (Visit 5)**

Subjects will also receive avatrombopag or placebo once daily for 5 days immediately following Chemotherapy Day. The following procedures will be performed on the last day of the 5-day post-chemotherapy IP treatment at Visit 5:

- Contact IRT;

- Perform ISTH bleeding assessment (see [Appendix D](#));
- Record concomitant medications;
- Assess adverse events;
- Collect blood samples for the following assessments:
  - Hematology (including platelet counts); and
  - Serum Chemistry;
  - Coagulation; and
  - PK sampling at pre-dose (within 30 minutes of IP dosing) and 0.5 to 2, 2 to 4, and 4 to 6 hours post-dose. Each sample must be collected at least one hour apart from adjacent samples.
- Assess chemotherapy dose modifications/schedule;
- Assess whether subject required platelet transfusion;
- Administer IP in the clinic with food after the first PK sampling;
- Review dosing diary; and
- Collect unused IP, if applicable.

### **6.3.3 Cycle X + 1 Days 11 ( $\pm 1$ day), 15 ( $\pm 1$ day), and 18 ( $\pm 1$ day) (Visits 6, 7, and 8)**

The following procedures will be performed on Cycle X + 1, Days 11, 15, and 18 at Visits 6, 7, and 8:

- Record concomitant medications;
- Assess adverse events;
- Collect blood samples for platelet counts;
- Assess chemotherapy dose modifications/schedule; and
- Assess whether subject required platelet transfusion.

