### **6.5.4 Cycle X + 3 Day 15 (±1 day) (Visit 16)**

For Cycle X + 4, this visit will be denoted Visit 16.1 and for Cycle X + 5, this visit will be denoted Visit 16.2. This numbering scheme will continue for subsequent enrolled open-label cycles. The following procedures will be performed on Cycle X + 3, Day 15 at Visit 16:

- Record concomitant medications;
- Assess adverse events;
- Perform ISTH bleeding assessment (see [Appendix D](#));
- Collect blood samples for platelet counts;
- Assess chemotherapy dose modifications/schedule; and
- Assess whether subject required platelet transfusion.

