- d. Chemotherapy Day may be 1 to 3 days depending on the subject's chemotherapy regimen (eg, if chemotherapy is given on Day 1 and Day 2, subjects will receive avatrombopag or placebo on Day 3). Avatrombopag or placebo will not be administered concurrently with chemotherapy on Chemotherapy Day. All assessments will occur on the first day of chemotherapy prior to chemotherapy dosing.
- e. Visit 5 will occur on the last day of the 5-day post-chemo IP treatment.
- f. Randomization must occur prior to IP dosing.
- g. Medical history to include tumor type, date of cancer diagnosis, and prior chemotherapeutic regimens (numbers of cycles, dates).
- h. Concomitant medications to include details of chemotherapeutic regimen (doses, schedule)
- i. Symptom-directed physical examination; full physical examination only required at Screening.
- j. Includes height (at the Screening Visit only), weight (Screening and Baseline Visits only), body temperature (Screening and Baseline Visits only), blood pressure, and pulse rate, and will be measured after resting for 5 minutes. Only screening vital signs will be recorded if screening and baseline visits occur the same day.
- k. Blood samples for PK analysis will be collected at the following time points: pre-dose and 0.5-2, 2-4, and 4-6 hours post-dose. A pre-dose PK sample will be collected within 30 minutes of IP dosing. Each PK sample must be separated by at least one hour from adjacent samples. Pharmacokinetic samples do not need to be collected at identical times for pre- and post-chemo visits.
- l. Hematology samples should be sent to the central lab in addition to local lab platelet counts at Visits 1, 2, 3, 4, and 5. Platelet counts at Baseline (Visit 2) may be performed prior (-1 day) to randomization. Only local lab platelet counts will be assessed at Visits 6, 7, and 8.
- m. Screening chemistries can be performed locally to determine eligibility. Chemistry samples will be sent to the central lab at Visits 1, 2, 4, and 5.
- n. For females of childbearing potential only. A serum or urine pregnancy test will be performed at the Screening Visit. At the Baseline Visit, the pregnancy test will be performed prior to IP administration.
- o. Urine or serum pregnancy test will be performed at the Baseline Visit.
- p. Assessment of bleeding will be performed if a subject has an unscheduled study visit.

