- Proportion of subjects who do not have major or non-major clinically relevant bleeding during the period after post-chemotherapy IP treatment in Cycle X+1 through Chemotherapy Day of Cycle X + 2

Subjects will be considered to NOT have major or non-major clinically relevant bleeding if no bleeding events were reported on the ISTH Non-surgical Bleeding Assessment CRF page that were classified as "Major Bleeding" or "Non-major clinically relevant bleeding" from the day after the last post-chemotherapy IP in Cycle X + 1 through the Chemotherapy Day in Cycle X+2. If information on the bleeding events is missing, subjects will be assumed to have had major or non-major clinically relevant bleeding during that period.

- Proportion of subjects who do not receive platelet transfusion during the period after post-chemotherapy IP treatment in Cycle X+1 through Chemotherapy Day of Cycle X + 2

Subjects will be considered to have not required a platelet transfusion if subjects did not require a platelet transfusion after taking the last post-chemotherapy IP in Cycle X + 1 through the Chemotherapy Day in Cycle X + 2. If information on platelet transfusion is missing, subjects will be assumed to have had a platelet transfusion during that period.

The categorical variables (eg, proportion) will be summarized and analyzed in the same manner as the primary efficacy endpoint. If the data is sparse where the

Confidential

approximative methods cannot be applied, the Fisher's Exact test will be used instead.

For continuous variables (eg, change from baseline in platelet count, duration of severe thrombocytopenia), the normality assumption of an analysis of covariance will be evaluated analytically using the Shapiro-Wilk test and visually using the residual plot.

Plots will be created displaying platelet count values over time separately for the Double-Blind/Observational period, the OLE period, and the entire study.

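### Protocol Section 6.3.3 leaves the ISTH bleeding assessment out of Visits 6 to 8 while Table 1 shows it as continuous, and the SAP counts only bleeds entered on the ISTH page

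*Protocol*

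**What the plan says.** **Visit text.** Protocol Section 6.3.3 opens with "The following procedures will be performed on Cycle X + 1, Days 11, 15, and 18 at Visits 6, 7, and 8". Five items follow: concomitant medications, "Assess adverse events", platelet counts, chemotherapy changes and platelet transfusion. The ISTH bleeding assessment is not among them. It is listed at Visits 2, 3, 4 and 5 (Sections 6.2.2, 6.2.3, 6.3.1, 6.3.2) and at Visit 9 (Section 6.4.1). At the open-label Day 15 visit, Section 6.5.4 includes "Perform ISTH bleeding assessment".

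**Schedule.** Table 1 in Protocol Appendix A, repeated in SAP Appendix A, shows the ISTH row as continuous, in a table whose last column is Visits 6 to 8. Its footnote p reads "Assessment of bleeding will be performed if a subject has an unscheduled study visit". Table 2 instead marks ISTH only at Visits 9 and 17.

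**Analysis rule.** SAP Section 8.2.1 sets the window "from the day after the last post-chemotherapy IP in Cycle X + 1 through the Chemotherapy Day in Cycle X+2". A subject is free of major or non-major clinically relevant bleeding when "no bleeding events were reported on the ISTH Non-surgical Bleeding Assessment CRF page" in those two classes. Missing bleeding information counts as having bled, but the SAP does not say what makes it missing.

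**Place in the testing order.** SAP Section 8.2.2 tests this endpoint at Step 3, two-sided 0.05. Platelet transfusion at Step 4 is tested only if Step 3 succeeds.

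**The concern.** Bleeding is a stated secondary objective, and this endpoint is part of the alpha-controlled hierarchy. The visit text drops the ISTH assessment at the three mid-cycle visits, breaking the pattern that the protocol keeps at the neighbouring visits and in the open-label period. A site working from the visit list would next complete an ISTH assessment at Visit 9 and rely on recall for the weeks before it.

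The analysis rule makes this matter. A bleed that never reaches the ISTH page does not count, and the SAP describes no step that carries a bleed recorded as an adverse event (AE) or adverse event of special interest (AESI) onto that page. Events lost equally from both arms shrink the observed difference at Step 3.

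**Working it through.** The plan states no figure for the bleeding endpoint, so there is none to reproduce. The check has three parts.

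**1. Timing.** Inputs: chemotherapy on Days 1 to c with c = 1, 2 or 3 (Protocol Section 3.1.2); five days of post-chemotherapy dosing with Visit 5 on the last day (Section 6.3.2); cycle length L = 21 or 28 (Section 4.1); Visit 9 on Day 1 of Cycle X+2 (Section 6.4.1). Dosing is assumed complete and cycles on time.

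- Visit 5 falls on Day c + 5, that is Day 6, 7 or 8.
- The window opens on Day c + 6, that is Day 7, 8 or 9.
- Visit 9 falls on Day L + 1, that is Day 22 or 29.
- On the visit text alone, the gap between ISTH assessments is (L + 1) − (c + 5) = L − c − 4 days.

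| Cycle length | c = 1 | c = 2 | c = 3 |
|---|---|---|---|
| 21 days | 16 | 15 | 14 |
| 28 days | 23 | 22 | 21 |

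Visits 6, 7 and 8 (Days 11, 15 and 18, each ±1) all lie after the window opens and before Visit 9. No other scheduled visit does. A delayed Cycle X+2 lengthens the gap. If post-chemotherapy dosing stops early or is not given, Visit 5 may itself fall inside the window.

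**2. Route of a mid-cycle bleed into the endpoint.** Take a non-major bleed on Day 13.

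- The subject mentions it at Visit 7 and the site completes an ISTH page: counted.
- The subject mentions it at Visit 7 and it is recorded only as an AE: not counted unless it is picked up at Visit 9, because SAP Section 8.2.1 reads the ISTH page and no reconciliation is stated.
- It is not mentioned until Visit 9 and is recalled then: counted.
- It is forgotten by Visit 9: not counted. A Visit 9 page reporting no bleeding is not obviously missing information, so the rule that missing means bled need not apply.

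**3. Illustrative power at Step 3.** Sample sizes are the planned 80 active and 40 placebo. Bleeding rates and the share missed are assumptions. The share missed, m, is taken as equal in both arms, so each rate is multiplied by (1 − m). Power is the exact unconditional probability that the unstratified Pearson (one-stratum CMH) test rejects at two-sided 0.05, summed over all pairs of binomial outcomes.

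| Assumed true bleeding, placebo vs active | m = 0 | m = 15% | m = 30% | m = 50% |
|---|---|---|---|---|
| 20% vs 5% | 71% | 63% | 55% | 43% |
| 25% vs 10% | 57% | 50% | 42% | 31% |

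For example, at 20% versus 5% with m = 30%, the observed rates are 0.20 × 0.7 = 14% and 0.05 × 0.7 = 3.5%. The difference drops from 15 to 10.5 percentage points and power from 71% to 55%.

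**The case against.** A reader might infer that the ISTH assessment is not done at all at Visits 6 to 8. The documents do not support that. Table 1 shows the row as continuous in both documents. Footnote p adds unscheduled visits and does not limit the row to them. Table 2 uses visit-only marks, so the schedule appears to separate the two modes of collection. Protocol Section 7 has the investigator evaluate bleeding by the ISTH definitions without limiting this to particular visits.

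There are also other ways to catch a bleed. AEs are assessed at each of Visits 6 to 8. Section 9.1.3 requires clinically significant bleeding to be reported as an AESI in every case. Many non-major clinically relevant bleeds would prompt an unscheduled visit, where footnote p applies. Visit 9 has an ISTH assessment inside the window, and missing information counts against the subject. All of this stands, and it rules out any claim that loss is certain or systematic.

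It does not remove the conflict. The open-label table also reads continuous, yet Section 6.5.4 still lists the assessment at Day 15, so the table entry was not treated there as a substitute for the visit instruction. Section 9.2 prefers open-ended AE questioning, whereas Appendix D separates non-major from minor bleeding on details such as a nosebleed lasting over 5 minutes or a skin hematoma over 25 cm², which open questions may not bring out. The AESI definition in Section 9.1.2 is not tied to the ISTH classes. Section 11.1.5 provides for general consistency checks but names no AE-to-ISTH check.

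A second tempting inference is that under-capture would block Step 4. It would only make failing Step 3 more likely. On the assumed rates, Step 3 power is 57% to 71% even with complete capture.

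**Conclusion.** The visit text and the schedule table disagree about three visits that carry much of the bleeding window, and the SAP rule gives no protection to a bleed that misses the ISTH page. That is an inconsistency worth correcting, not proof that the assessment is omitted. The firm results are the gaps of 14 to 16 days (21-day cycle) or 21 to 23 days (28-day cycle) when the visit text alone is followed, given full dosing and on-time cycles. The direction is also clear: equal under-capture shrinks the Step 3 difference and makes it less likely that Step 4 is reached. The size of any power loss is unknown, because the documents give no bleeding rates and no basis for a miss rate; the tabulated figures are illustrations. One limit on the reading is that the exact extent of the arrow in Table 1 cannot be seen in the extracted text. The point is a cheap improvement to a key secondary endpoint.

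**What to change.** - **Protocol Section 6.3.3:** add the ISTH bleeding assessment (Appendix D) at Visits 6, 7 and 8, covering the time since the previous visit.
- **Table 1, in the protocol and in the SAP copy:** mark Visits 6 to 8 so that text and schedule agree.
- **SAP Section 8.2.1:** require every bleeding AE or AESI in the window that has no ISTH page to be queried and given an ISTH classification before unblinding. State when bleeding information counts as missing.

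At nominal visit days with one-day chemotherapy, assessments would then fall on Days 6, 11, 15, 18 and 22 or 29. The longest gap becomes 11 − 6 = 5 days in a 21-day cycle and 29 − 18 = 11 days in a 28-day cycle, instead of 16 and 23.

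The cost is a few minutes at visits that already take place and a small amount of data review. No visit or staff is added, and sample size and alpha do not change.
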